8.1.2. Adjudication Committee

An adjudication committee will review the standardized endogenous creatinine clearance data on a case-by-case basis for part 1 patients in the same way as for the part 2 data review to determine the values to be used in the analysis. The adjudication committee will be provided with a data listing of collection time of urine and blood creatinine, their results as well as the calculated standardized endogenous creatinine clearance (more details are included in the adjudication committee charter). Additionally the adjudication committee will be provided with a data listing of collection time or urine urea nitrogen, volume of urine and BUN as well as the calculated value for urea clearance. The adjudication committee will also be provided with patients figures for standardized creatinine clearance and urea clearance.

The adjudication committee will then indicate for each record if the standardized endogenous creatinine clearance is acceptable (i.e. can be used in the analysis) and provide

comments (if applicable). PPD Biostatistics will use the standardized endogenous creatinine clearance deemed acceptable by the adjudication committee to re-derive the AUC₁₋₇.

8.1.3. Assumption Testing

The underlying assumptions for ANOVA (normality and homogeneity of variance of the studentized residuals) will be investigated at the Part 1 interim analysis and at the Part 2 analysis by examining a normal probability plot of the residuals and a plot of the fitted values against the residuals. These results will be presented as a SAS[®] output.

Should there be a strong indication that these assumptions are not satisfied, a corresponding non-parametric analysis will be conducted to calculate the p-values for interim analysis at Part 1 and at Part 2 (i.e., using ANOVA with the rank-transformed values of AUC₁₋₇ as the outcome variable and treatment and site as explanatory variables).

8.1.4. Sensitivity Analyses

The interim analysis was conducted on non-adjudicated data, so will be repeated using only the data deemed acceptable by the adjudication committee, therefore a sensitivity analysis will be performed on the primary endpoint using adjudicated Part 1 data.

In order to investigate the effect of imputing the missing data with LOCF, a sensitivity analysis will be conducted on the primary efficacy endpoint. The ANOVA analysis will be performed as described in [Section 8.1.1](#) but excluding any patients that died prior to Day 8 of the study. The descriptive statistics for the primary endpoint will also be repeated for this sensitivity analysis.

In addition, the ANOVA analysis (as described in [Section 8.1.1](#)) will be repeated including as additional covariates the baseline serum creatinine results and the baseline APACHE II score for the ITT Combined Set for the optimal recAP dose and Placebo. If the analysis does not converge, APACHE score will be categorized into two categories (< 25, ≥25).

Finally, the area under the time-corrected endogenous creatinine clearance curve from Day 5 to Day 7 (AUC₅₋₇) will be derived and analyzed with an ANOVA as described in [Section 8.1.1](#) to determine if the AUC₅₋₇ is a predictor of treatment effect.

AUC₅₋₇ is calculated as the average of the standardized endogenous creatinine clearance values over the 3 days. Specifically, denoting C_i as the standardized endogenous creatinine clearance on Day i , AUC₅₋₇ is defined as:

$$AUC_{5-7} = \frac{1}{3} \sum_{k=5}^7 C_i$$

Any missing C_i values will be handled by linear interpolation where possible, otherwise they will be imputed by last observation carried forward (LOCF). When there are no preceding post-baseline measurements to use, the baseline measurement from Day 0 (i.e., prior to treatment) will be carried forward. If there are missing values the values imputed for deriving AUC_{1-7} will be used to derive AUC_{5-7} .

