Sepsis-associated acute kidney injury (SA-AKI) is a serious condition with a mortality rate of up to 70%, while patients surviving an episode of acute kidney injury (AKI) are at risk of developing chronic kidney disease (CKD) ([Oppert et al 2008](#); [Chawla et al 2011](#), [Vaara et al 2012](#)).

As there are no guidelines for the development of drugs for the indication SA-AKI the proposed design of this study was determined to be optimal by a group of leading global experts in AKI and sepsis, and subsequently was discussed (and agreed) with European and United States regulatory agencies.

The study has been set up with an adaptive study design including 2 parts, with dose selection based on an interim analysis after all patients in Part 1 have completed the first 7 days of the study, unless the patient was randomized but died or discontinued prior to completing 7 days. The 3 doses proposed in Part 1 are selected based on a combination of information from previous clinical studies conducted with bovine intestinal alkaline phosphatase (BiAP), and pre-clinical animal models and pharmacokinetic (PK) modeling and simulation in a Phase I healthy volunteer study with recombinant human AP (recAP). Assuming comparable safety profiles, the most optimal dose will be selected at the interim analysis by an independent data monitoring committee (DMC). The primary endpoint, creatinine clearance, was chosen because as a continuous variable it is sensitive for detecting relatively small treatment effect differences of recAP versus placebo, as well as determination of effect size differences between the different dosages. Incidence of dialysis, considered to be a relevant clinical endpoint for Phase 3 pivotal studies, was chosen as the key secondary endpoint. In Part 1 PK samples will be taken to assess the pharmacological properties of recAP in patients, in addition to the information previously derived from the healthy volunteers.

Currently there is no treatment available for SA-AKI; hence, recAP is considered as add-on therapy and with that the use of a placebo arm is fully justified.

Following patients up to a period of 90 days allows for assessing potential disease-modifying characteristics of recAP in kidney function (occurrence or worsening of CKD).

2. Objectives

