Please note that any patients who do not receive any dose of study drug will be excluded from the safety and PP analyses, and therefore do not need to be considered in the [Table 4-1](#). Dose windows were constructed in line with the weight ranges and corresponding pre-calculating volumes displayed in [Table 15-3](#). See [Section 15.3](#) for full justification of these windows.

Statistical Analysis

All statistical tests will be two-sided and performed using a 5% significance level, displaying 95% two-sided confidence intervals (CIs), unless specifically stated otherwise. As the primary efficacy endpoint is analyzed at the interim analysis and at the end of the study, multiplicity will be addressed by using a combination test to combine the results (see [Section 8.1.1](#)). A hierarchical method will be employed to address any multiplicity arising from the analysis of the key secondary endpoint. In other words, the formal analysis of this endpoint will be performed only if a statistically significant result is obtained from the combination test analysis of the primary endpoint. All analyses performed on the other secondary endpoints are for exploratory purposes only; therefore, no further multiplicity adjustment is required.

All analyses will be undertaken using SAS[®] Version 9.2 (SAS Institute, Inc, Cary, North Carolina) or later.

Weight

Body weight (in kg or lb) will be measured or estimated at screening. Weight will be displayed in kg and derived from lb as:

$$Weight[kg] = \frac{Weight[lb]}{2.2046}$$

Temperature

Temperature (in °C or °F) will be measured from Day 1 – Day 28. Temperature will be displayed in °C and derived from °F as:

$$Temperature[°C] = \frac{Temperature[°F] - 32}{1.8}$$

Laboratory Data

For laboratory data that are recorded as values of '<x' and '>x' where x is any numeric value, the numeric part after the '>' and '<' (i.e. x) will be used for summarizing and in graphical presentations. In addition the numeric part will be used in the derivation of the quartile-based subgroup definitions.

In the tables where serum creatinine or CRP data are presented, if a subject has missing baseline central laboratory measured serum creatinine or CRP values, but has available baseline local laboratory measured values then the local laboratory values will be used to

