4.1. Sample Size

A sample size of $n_1 = 30$ patients per treatment group in Part 1 with an additional $n_2 = 85$ patients recruited to each of the optimal recAP dose and placebo treatment groups in Part 2 (for a total sample size of $n = 290$ patients) is planned. Recruitment will continue during the interim analysis, so the total number of patients will exceed 290. Custom programmed simulations were performed using SAS[®] Version 9.2 (SAS Institute, Inc, Cary, North Carolina) to determine power and type I error rate of the chosen sample size and design under a number of different dose response scenarios. Each scenario assumed a standard deviation of 49 mL/min for the primary endpoint (area under the time-corrected endogenous creatinine clearance curve from Day 1 to Day 7 [AUC₁₋₇]) with an assumed response of 60 mL/min for the placebo group, and between 60 mL/min (no treatment effect) and 79 mL/min (strong treatment effect) for the recAP dose groups.

Fifty-thousand simulations were performed to show that the 1-sided type I error rate is 2.4% (and hence is well controlled at the 1-sided 2.5% significance level). The power was defined as the probability of rejecting the null hypothesis (of no difference between treatment groups) when 1 or more recAP dose groups have an effective treatment effect, defined as a response of 69.5 mL/min. This was investigated across 7 scenarios with 10 000 simulations performed for each. In the most realistic scenarios (with strong treatment effects, i.e., responses of 79 mL/min for the medium and high recAP dose groups and a varying response of between 60 mL/min and 79 mL/min for the low-dose group) the chosen design achieved power of between 79% and 86%. This dropped to 66% to 67% for other scenarios where only the high recAP dose group had a strong treatment effect.

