8.1.1. Primary Analysis

The primary efficacy analysis will be an analysis of variance (ANOVA) of the area under the time-corrected endogenous creatinine clearance curve from Day 1 to Day 7 with treatment and site as explanatory variables.

For all patients recruited up to the interim analysis, the primary efficacy analysis will be conducted for the ITT Combined Set at the interim analysis (which is identical to the ITT Part 1 Interim set at the time of the interim analysis) where AUC_{1-7} will be compared between the 3 active treatment groups and placebo. This analysis will be considered in conjunction with the safety data to determine the optimal recAP dose for use in Part 2.

The primary efficacy analysis will be conducted for the ITT Part 2 Set, PP Day 1 – 7 Part 1 and PP Day 1 – 7 Part 2 Set where AUC_{1-7} will be compared between the optimal recAP dose and placebo (for the PP Day 1 -7 Combined Set, each dose of recAP will be compared to Placebo). Also, all doses combined will be compared to Placebo.

Confirmatory testing of the single hypothesis comparing optimal dose with placebo will be based on a closed-testing procedure. This hypothesis will be rejected at the 5% significant level if it and all intersection hypotheses involving it are all rejected at the 5% significance level. The testing strategy used to combine results from Parts 1 and 2 will be a combination test based on the inverse normal method, with the test statistic of the combination test calculated as ([Bauer and Köhne 1994](#)):

$$\sqrt{\frac{n_1}{n}} \Phi^{-1}(1 - p_1) + \sqrt{\frac{n_2}{n}} \Phi^{-1}(1 - p_2)$$

where n_1 and n_2 are the sample sizes per group in interim analysis at Part 1 and in Part 2, respectively, $n = n_1 + n_2$, Φ refers to the standard normal distribution, and p_1 and p_2 are the one-sided p-values from interim analysis at Part 1 and from Part 2, respectively. For the intersection hypotheses, p_1 is the Dunnett adjusted one-sided p-value in Part 1 (for the optimal dose selected), and p_2 is the one-sided unadjusted p-value to compare optimal dose with placebo in Part 2 for all hypotheses.

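### SAP 8.1.4 says an ANOVA of AUC5-7 will show whether AUC5-7 predicts treatment effect, but that model only compares mean Day 5-7 clearance between arms

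*SAP*

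**What the plan says.** The last analysis in SAP Section 8.1.4 concerns AUC5-7, which "is calculated as the average of the standardized endogenous creatinine clearance values over the 3 days". It "will be derived and analyzed with an ANOVA as described in" Section 8.1.1, and the sentence closes with the aim of establishing whether AUC5-7 "is a predictor of treatment effect".

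Section 8.1.1 defines the ANOVA as a model for the area under the clearance curve "with treatment and site as explanatory variables". The general testing rule in SAP Section 4 is: "All statistical tests will be two-sided and performed using a 5% significance level".

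The SAP gives no criterion for deciding that AUC5-7 is, or is not, a predictor. The statistical section of the protocol (Section 7) does not mention AUC5-7.

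**The concern.** The stated purpose and the stated method do not match. A predictor of treatment effect would ordinarily be one of two things:

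- a marker whose treatment difference carries information about the effect on a later outcome (surrogacy);
- a variable that identifies patients in whom the treatment effect is larger (effect modification).

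The first needs a model that links AUC5-7 to a later outcome. The second needs an interaction with treatment, and AUC5-7 is in any case measured after treatment. The planned ANOVA has neither.

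What is at stake is one sentence in the study report. Followed literally, the SAP lets a significant ANOVA be reported as showing that late clearance is a predictor, and a non-significant one as showing that it is not. Neither statement would have been tested.

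**Working it through.** **Step 1: which question each model can answer.**

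- Section 8.1.4, AUC5-7 analysis: outcome AUC5-7; terms treatment and site. The treatment null is equal mean AUC5-7 in the arms.
- Section 8.1.4, covariate-adjusted analysis: adds baseline serum creatinine and baseline APACHE II. AUC5-7 is not a term.
- Section 8.1.5, supportive factors: baseline biomarkers, AKIN stage, type of infection, baseline eGFR, time from diagnosis and APACHE II. AUC5-7 is not on the list.
- Section 8.2.1, RRT incidence: logistic regression on treatment and site, repeated with the 8.1.5 factors. AUC5-7 is not a term.
- Section 8.2.2.1, days on RRT: ANOVA on treatment and site.
- Section 8.3, composite endpoints: logistic regression on treatment and site.

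AUC5-7 appears only as an outcome. The mismatch therefore rests on the text and needs no number.

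**Step 2: the plan's own figures.** The documents give no power or SD for AUC5-7. The nearest stated figure is the power of the adaptive AUC1-7 design, 79% to 86% in the scenarios called most realistic. Inputs from SAP Section 4.1: "Each scenario assumed a standard deviation of 49 mL/min for the primary endpoint", "assumed response of 60 mL/min for the placebo group", 79 mL/min for a strong effect, 30 per arm in Part 1 and 85 per arm in Part 2. A simulation used selection of the best dose, the inverse normal combination with weights √(30/115) and √(85/115), a Dunnett-adjusted Part 1 p-value, one-sided 2.5%, and futility when all three p-values exceed 0.8. Site was ignored. With placebo, low, medium and high means in that order:

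- 60, 69.5, 79, 79: 79.3%
- 60, 60, 79, 79: 81.3%
- 60, 79, 79, 79: 85.6%

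The stated range is reproduced. The simulated one-sided type I error is 2.50% against 2.4% stated, a gap of about 1.4 Monte Carlo standard errors at 50,000 runs (standard error about 0.07 points). Nothing is wrong with the primary design on this account.

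**Step 3: how the AUC5-7 comparison behaves.** Assumptions: AUC5-7 has the SD of 49 and the effect of 19 (79 − 60) given for AUC1-7; one two-arm test; site and dose selection ignored. Section 8.1.4 does not say which analysis set applies or whether the Part 1/Part 2 combination carries over, so two sizes are shown.

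- 85 per arm: standard error 49 × √(2/85) = 7.52; 19/7.52 = 2.53; exact two-sided t-test power 71.0%.
- 115 per arm: standard error 49 × √(2/115) = 6.46; 19/6.46 = 2.94; exact power 83.3%.

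Next, a hypothetical later outcome was added, with within-arm correlation 0 or 0.5 with AUC5-7 (20,000 runs, 85 per arm). Rejection rates at 5%:

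| True shift in AUC5-7 | Correlation with later outcome | Planned comparison | Direct association test |
|---|---|---|---|
| 19 | 0 | 70.2% | 5.3% |
| 19 | 0.5 | 70.7% | 100% |
| 0 | 0 | 4.8% | 5.3% |
| 0 | 0.5 | 4.9% | 100% |

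The planned comparison responds to the treatment shift and not to the correlation. The first column of results is the power and size of a valid test of its own null. The result carries no information on prediction.

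**Step 4: overlap with the primary endpoint.** AUC5-7 uses three of the seven days in AUC1-7. With equal variances and a common day-to-day correlation r (assumed), their correlation is √[3(1 + 6r) / (7(1 + 2r))]. This gives 0.65 at r = 0, 0.93 at r = 0.5 and 0.99 at r = 0.9. Agreement between the two analyses is largely built in. That is normal for a sensitivity analysis, but it is not separate evidence.

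**The case against.** The strongest reply is that the phrase is merely loose. The analysis sits among the sensitivity analyses of the primary endpoint, keeps the primary model and shortens the window. Read that way, it asks whether the treatment effect is visible in Days 5 to 7, and the ANOVA answers that properly. This largely stands: the analysis is sound and only its description is wrong. The words still say something else and should be changed.

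Three stronger readings are tempting, and the documents do not support them.

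- A reader might set 71% or 83% against the nominal 5% and infer an inflated false-positive rate. Those figures are power under a true 19 mL/min shift; with no shift the rate is about 5%. The inputs for AUC5-7 are also assumed.
- A reader might infer that the choice of a Phase 3 endpoint hangs on this result. The stated objectives (SAP Section 2.1) are the effect on renal function and the therapeutic dose for Phase 3. On the endpoint, SAP Section 1 already says: "Incidence of dialysis, considered to be a relevant clinical endpoint for Phase 3 pivotal studies, was chosen as the key secondary endpoint". No passage makes a decision depend on AUC5-7, and treatment is compared directly on RRT, the composites and mortality.
- A reader might infer that a regression of later RRT on AUC5-7 and treatment must be added. That would test whether AUC5-7 is prognostic, not whether it predicts treatment effect. Part of the association would be built in, because the RRT start and stop criteria in protocol Section 6.3.9 use urine output, creatinine and creatinine clearance.

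That a report would misstate the result is an inference from the purpose clause; no decision rule is written.

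**Conclusion.** The point holds as a mismatch between stated purpose and method. The ANOVA in Section 8.1.4 tests a difference in mean Day 5-7 clearance and supports no conclusion about prediction, whether significant or not. This follows from Sections 8.1.1 and 8.1.4 and does not depend on the assumed SD, effect or correlations, which only illustrate it.

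The size is small. The analysis is outside the confirmatory hierarchy, and AUC5-7 is not among the outputs listed for the interim analysis in SAP Section 11. The primary test, its type I error, the power and the dose selection do not change.

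**What to change.** In SAP Section 8.1.4, delete the purpose clause that ends in "is a predictor of treatment effect". In its place, state that this sensitivity analysis estimates the treatment effect on late (Day 5-7) creatinine clearance, and that no claim of prediction or surrogacy will be drawn from it.

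The cost is one sentence of SAP text. No new data, model or change to the programmed ANOVA is needed.

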8.1.5. Supportive Analysis for the Primary Efficacy Endpoint

Due to the high variability of the creatinine clearance, the change from baseline in serum creatinine at Day 7 will be analyzed using an ANOVA with baseline serum creatinine, treatment (optimal recAP dose and placebo) and site as explanatory variables. The analysis will be run on the ITT Combined Set. If there is more than one serum creatinine result collected at Day 7, the average at Day 7 will be used to derive the change from baseline.

Additionally the primary endpoint analysis will be repeated with the following variables as additional factors within the ANOVA model for the ITT Combined Set (for the optimal recAP dose and placebo):

- Baseline biomarkers for kidney function:
 - Fractional excretion of sodium (<1%, ≥1 % - ≤2%, >2%).
 - Fractional excretion of urea (<35%, ≥35%).
- Baseline AKIN stage (stage 1, stage 2 and stage 3).
- Microbial infection. The following are the five possible outcomes:
 1. Gram positive
 2. Gram negative
 3. Mix gram positive/gram negative
 4. Other (e.g. fungal)
 5. Unknown.

If a blood culture is available this is leading. (Note that if a staphylococcus epidermis is the outcome this is a contamination and should be ignored). If no blood culture is available, the culture from the site for which the patient was hospitalized (index indication) is leading e.g. patient hospitalized for lung infection, with positive sputum and positive urine culture: sputum is then leading.

- Baseline urinary biomarkers for proximal tubular cell damage:

- KIM-1 (<Q1, ≥Q1 - <Q2, ≥Q2 - <Q3, ≥Q3).
- IL-18 (<Q1, ≥Q1 - <Q2, ≥Q2 - <Q3, ≥Q3).
- GST-alpha (<Q1, ≥Q1 - <Q2, ≥Q2 - <Q3, ≥Q3).

For GST-alpha, two different kits were used in the testing of GST-alpha therefore quartiles will be calculated separately for each kit and then for each subject, their baseline value will be compared against the quartile for the kit that was used to assess their GST-alpha baseline result. The resulting assigned quartile categories will then be combined together for subgroup summaries regardless of which kit was used.

- Baseline biomarkers for systemic inflammation:
 - IL-6 (<Q1, ≥Q1 - <Q2, ≥Q2 - <Q3, ≥Q3).
 - CRP (<Q1, ≥Q1 - <Q2, ≥Q2 - <Q3, ≥Q3).
 - LBP (<Q1, ≥Q1 - <Q2, ≥Q2 - <Q3, ≥Q3).
- Baseline eGFR by CKD-EPI formula (<Q1, ≥Q1 - <Q2, ≥Q2 - <Q3, ≥Q3).
- Time from first diagnosis of SA-AKI to start of recAP treatment (0 to <6 hours, 6 to <12 hours, 12 to <18 hours, 18 to <24 hours, ≥24 hours).
- Baseline APACHE II score (<25, ≥25).

Summaries will be produced with these factors as by variables.

All subgroup analyses will be exploratory; meaning that no adjustment for multiplicity is required.

A table will be produced for the ITT Combined Set displaying the number and percentage of patients included in each subgroup/factor category, by treatment group (optimal recAP dose and placebo). This will be repeated for the ITT Part 1 Interim Set and the ITT Part 2 Set.

